Appendix G: Data Collection Method (EDC)

Sponsor/Investigators are required to prepare and maintain adequate and accurate case histories designed to record all observations and other data pertinent to the investigation on each subject. Source documents include all original records from which eCRFs derive their data.

Access to eCRF application

The eCRF application is accessed through the internet and requires the use of a personal user account and password.

The following documents and information are required prior to receipt of personnel user account and password:

- Current signed and dated CV
- Completed Signature and Delegation List
- Documented training
- Email address and telephone

Personal user account and password are provided via email. User account and password are confidential and personal. They are not to be shared with other people.

The first time the application is accessed, the password will need to be changed. If the password is forgotten and/or lost, a new password can be provided via email by following the instructions on the webpage.

Each center must be authorized to start enrolling patients in the investigation before access privileges to the application is made available.

Access privileges are based on the tasks assigned on the Signature and Delegation List and will be either:

- Data entry and review
- Data entry, review and sign off

All eCRFs are completed, saved ('save complete') and approved by an investigator in a timely manner.

Appendix H: List of Case Report Forms

Data Points Provided Under Separate Cover

- Screening: Inclusion/Exclusion Criteria
- Baseline/Medical History Form
- Physical Assessment/Office Blood Pressure Form
- 24 Hour Ambulatory Blood Pressure Form
- Echocardiography Form
- Blood/Urine Lab Form: Serum Creatinine, eGFR, Hemoglobin A1c, Fasting Glucose, Fasting Insulin and Albumin-Creatinine Ratio
- Renal Artery Evaluation Form
- Procedure Form
- Post Procedure and Discharge Form
- AF Recurrence Form
- Adverse Event Form
- Death Form
- Deviation Form
- Termination Form

	2.6 Other Analyses	
	2.7 Analysis Software	

#### 1 INTRODUCTION

#### 1.1 Purpose

The purpose of this Statistical Analysis Plan is to provide guidance for analyses associated with the RD+AF Clinical Trial (Agile# SJM-CIP-0009).

#### 1.2 Scope

This plan describes the study specific statistical analyses required for the RD+AF trial.

#### 1.3 Definitions

Role/Term	Definition
SJM Clinical Team	Those individuals working within the GCAO clinical affairs department at the
(SJMCT)	project manager level or lower (e.g. Clinical Project Manager, CRAs, CRCs,
	etc.)
Field Clinical	Those individuals providing EnligHTN procedure training, case coverage,
Engineers (FCE)	and other administrative support. For the purposes of this document, this
	refers to FCE Directors, FCE Managers, and all other levels of FCEs that have been assigned to work on the RD+AF trial.
Monitor	This is a subset of the SJM personnel or CRO personnel who have received
	monitoring training outside of this plan. They are responsible for oversight
	of specific study sites and will be performing on-site monitoring visits. They
	may or may not be part of the SJMCT.
Site Personnel (Site)	Those individuals working as part of the RD+AF trial as an employee or agent of the study site.
Data Management	Those individuals working within the Data Management group at SJM in the
Personnel (DM)	GCAO (e.g. database developers and report programmers)
Vendor (V)	Any non-study site entity outside of SJM that has been contracted to
	perform services or provide equipment for study execution.
Statistics (Stats)	Those individuals within the Biostatistics group at SJM in the GCAO that are
	involved with the trial.
Safety Personnel	Those individuals within the Clinical Safety group of the GCAO at SJM that
(Safety)	are involved with analysis and reporting of adverse events.
Regulatory (Reg)	Those individuals within the Regulatory Affairs group at SJM in CATD that
	are involved with the trial.
Trial Master File (TMF)	Electronic files kept in Windchill

For any other terms, please consult the RD+AF clinical investigation plan (#SJM-CIP-0009).

#### 2 STATISTICAL ANALYSIS

#### 2.1 Study design

This is a post market, prospective, multicenter, 2:1 randomized study of the EnligHTN™ Renal Denervation System in conjunction with atrial fibrillation ablation. Up to one hundred subjects with paroxysmal or persistent atrial fibrillation and uncontrolled hypertension will undergo atrial fibrillation ablation. Per the 2:1 randomization, a minimum of 50 or 2/3 of the total patient cohort will also undergo renal artery ablation. Subjects will be followed up to two (2) years post procedure.

To assess the feasibility of concomitant cardiac ablation for the treatment of atrial fibrillation and renal denervation ablation using the EnligHTN renal denervation system in achieving freedom from atrial fibrillation in patients with hypertension. Freedom from atrial fibrillation

will be assessed based on electrocardiographic data during nine months following the blanking period.

#### 2.2 Sample size estimation

The sample size of 75 patients is used considering the study purpose: to complete a preliminary evaluation on whether or not concomitant renal denervation with the EnligHTN™ Renal Denervation System and cardiac ablation will result in improved outcomes as compared to ablation alone in patients being treated for Atrial Fibrillation. Of these patients, a minimum of 50 patients (or 2/3 of the total patient cohort) will undergo both a cardiac ablation procedure and a concomitant renal denervation procedure.

No formal power analysis or hypothesis test will be performed. However the data collected will be analyzed and presented using the descriptive or appropriate summary statistics.

All patients who have signed a Patient Informed Consent (PIC) will be considered enrolled in the study.

However, the Primary Analysis population will only include those patients that have signed a PIC, have undergone a cardiac ablation procedure for the treatment of atrial fibrillation, and, if in the renal denervation arm of the study, had the EnligHTN™ Renal Denervation System enter his/her body.

It is anticipated that there may be subjects who have been enrolled in the study but are not included in the Primary Analysis population, such as:

- Subjects who are enrolled but do not meet baseline inclusion or exclusion criteria before the procedure; these are considered the screen failure population.
- Procedurally excluded populations will include subjects who have enrolled in the study and start the procedure, but do not undergo a cardiac ablation procedure for the treatment of atrial fibrillation or if in the renal denervation arm of the study and do not have the EnligHTN™ Renal Denervation System enter his/her body, due to their anatomy, circumstances related to the procedure, or physician judgment.

Subjects who withdraw from the investigation will not be replaced in any analysis population. All available data from these subjects will be included in summary statistics and analyses where applicable.

#### 2.3 Data Analysis and Reporting

Data analysis will be performed across all subjects based on Primary Analysis population unless otherwise specified.

The data collected will be presented using the appropriate summary statistics. Continuous data will be summarized using descriptive statistics (mean, number of observations, standard deviation, minimum and/or maximum values) and categorical data will be summarized using frequencies and percentages.

#### 2.4 Primary objective

The primary objective is to assess the feasibility of concomitant cardiac ablation for the treatment of atrial fibrillation and renal denervation ablation using the EnligHTN renal denervation system in achieving freedom from atrial fibrillation in patients with hypertension.

Project Code: SJM-CIP-0009 Project Name: RD+AF

The freedom from atrial fibrillation will be assessed based on electrocardiographic data during nine months following the blanking period including the one week recording coinciding with the 12 month follow-up visit (9 months following the 3 month blanking period). AF recurrence during the blanking period will not qualify as an endpoint event per protocol. Subjects may be re-treated with up to two repeat ablation procedures during the course of the study with a 3 month blanking period following the treatment. Assessment of the AF recurrence will be determined through evaluation of 12 lead ECG recordings, holter monitoring or event recorder results. AF Recurrence is defined as episodes lasting longer than 30 seconds in duration unless detected via 12-lead EKG. To count as a study-related recurrence, the AF episode must be documented on the AF Recurrence Evaluation CRF. For this study, AF also includes (documented >30 seconds) atrial flutter and atrial tachycardia.

No formal hypothesis testing will be performed. An overall percentage of subjects experiencing an event will be summarized for each randomization arm and is defined as:

Number of subjects with AF recurrence within 12 months post procedure Number of subjects with at least 12 months of follow – up or experienced AF recurrence \* 100

Subjects who exit the study prior to 12 month visit without AF recurrence will be excluded from the percentage to prevent under-estimation of the event rate. Kaplan-Meier analysis may be performed to provide freedom from atrial fibrillation rates at one year for each randomization arm using date of ablation procedure to date of first event.

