4.6 Blanking Period

For three months following the ablation procedure, the subject is in a blanking period while the cardiac tissue recovers from the RF energy application. The AF recurrences during the blanking period will not be reported. If recurrence occurs after the blanking period, the subject will be considered a 'recurrence' according to the primary efficacy endpoint.

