4.8 Re-treatment of AF

Subjects experiencing recurrent atrial arrhythmias may be treated with up to two repeat ablation procedures during the course of the 24 month study. This includes ablation of cardiac arrhythmias that may be responsible for initiating or maintaining atrial fibrillation. The subject's follow-up window will not be re-set, but there will be a 3 month blanking period following the retreatment procedure.

Re-treatment procedures will follow the ablation procedure as outlined previously in section 4.4, but additional information regarding the completeness of the initial ablation lesions will be recorded. Specifically, entrance and exit block from the pulmonary veins and completeness of any additional lesions lines that were placed will be recorded prior to any new RF energy being delivered. Pre-procedure requirements are at the discretion of the Investigator.

Repeat ablation procedures will count towards the recurrence but will not reset the follow up period. Such patients will continue to be a part of the study and adverse event data will be collected on them throughout their participation in the study.

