#### 2.5.3 AF Recurrence

The primary endpoint will evaluate recurrence of AF during the 9 months following the blanking period for each group. Secondarily, the recurrence of AF based on electrocardiographic data at 3 months, 6 months and 24 months post procedure will also be reported by group. The rate of AF recurrence will be calculated using the same definition as the primary objective for the specified time points.

 Assessment of the AF recurrence will be determined through evaluation of 12 lead ECG recordings, holter monitoring or event recorder results. AF Recurrence is defined as episodes lasting longer than 30 seconds in duration unless detected via 12 Lead EKG. To count as a study-related recurrence, the AF episode must be documented. For this study, AF recurrence also includes (documented ≥30 seconds) atrial flutter and atrial tachycardia.

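### Protocol 4.8 counts a repeat ablation towards recurrence, but the definitions in the protocol's analysis sections and SAP 2.4 count only a documented episode

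*SAP*

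**What the plan says.** **Protocol 4.8.** Re-treatment is allowed: "Subjects experiencing recurrent atrial arrhythmias may be treated with up to two repeat ablation procedures during the course of the 24 month study". Each repeat is followed by a new 3-month blanking period. The counting rule is: "Repeat ablation procedures will count towards the recurrence but will not reset the follow up period".

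**Protocol 4.6**, on the initial blanking period: "The AF recurrences during the blanking period will not be reported". A recurrence after that period makes the subject a recurrence for the primary endpoint.

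**Protocol 4.7, 4.10.10, 7.4.1 and 7.4.2.3.** Recurrence is a documented episode of AF, flutter or atrial tachycardia of about 30 seconds or more. Section 4.7 exempts 12-lead ECGs from the duration requirement. None of the four mentions repeat ablation.

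**SAP 2.4.** It repeats the allowance for further ablation: "with up to two repeat ablation procedures during the course of the study with a 3 month blanking period following the treatment". It defines the event by an episode, exempts 12-lead ECGs from the duration threshold, and adds: "To count as a study-related recurrence, the AF episode must be documented on the AF Recurrence Evaluation CRF". The numerator is subjects with AF recurrence within 12 months. The denominator is subjects with at least 12 months of follow-up or a recurrence. On early exits: "Subjects who exit the study prior to 12 month visit without AF recurrence will be excluded from the percentage to prevent under-estimation". The optional Kaplan-Meier analysis runs from the ablation to the first event and does not name repeat ablation as an event.

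**SAP 2.5.3**, for 3, 6 and 24 months: "The rate of AF recurrence will be calculated using the same definition as the primary objective for the specified time points".

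**The concern.** SAP 2.4 adopts the parts of 4.8 that permit re-ablation and that stop later episodes from counting for three months. It leaves out the part that makes the re-ablation itself count. A subject who needed a second ablation in the endpoint period could therefore appear in the main result as free of AF.

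The study is descriptive: both documents rule out a power analysis and a hypothesis test, so no error rate or sample size depends on this. The per-arm recurrence percentage is, however, the main result. The omission can only lower it relative to 4.8, although SAP 2.4 drops early exits in order to avoid under-estimating the event rate.

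**Working it through.** **1. The definitions side by side**

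| Place | What makes a recurrence | Repeat ablation |
|---|---|---|
| Protocol 4.6 | Recurrence after initial blanking | Not mentioned |
| Protocol 4.7, 4.10.10, 7.4.1, 7.4.2.3 | Documented episode | Not mentioned |
| Protocol 4.8 | – | Permitted, re-blanked, and counts |
| SAP 2.4 | Episode on the AF recurrence form | Permitted and re-blanked; counting rule absent |
| SAP 2.5.3 | Definition of SAP 2.4 | Absent by inheritance |

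**2. Can a re-ablated subject lack a countable episode?**

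Yes, by a narrow route. Section 4.8 permits a repeat for recurrent atrial arrhythmias and does not require that these fall after blanking. AF seen only in the first 3 months is not counted (protocol 4.6 and 7.4.1, SAP 2.4). The subject may then be re-ablated after month 3. Section 4.8 leaves pre-procedure requirements for a repeat to the investigator, so a fresh qualifying recording is not assured. If none is made before the repeat and no countable episode is documented later, there is no event under SAP 2.4.

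**3. How each subject is classified**

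| Re-ablated subject | SAP 2.4 | Protocol 4.8 |
|---|---|---|
| Countable episode after initial blanking | Recurrence | Recurrence |
| Repeat after initial blanking, no countable episode, followed 12 months | AF-free | Recurrence |
| Same, but exits before 12 months | Excluded from the percentage | Recurrence |
| Repeat inside initial blanking, no countable episode | AF-free or excluded | Unclear: 4.8 has no time limit, 4.6 does not count AF in this period |

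The finding rests on the second and third rows.

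**4. Weight of one subject followed to 12 months**

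The denominator is the same under both rules, so the shift is 100/n points. With the SAP total of 75 at 2:1, the arms are 75 × 2/3 = 50 and 75 − 50 = 25.

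- Denervation arm: 100/50 = 2.0 points
- Control arm: 100/25 = 4.0 points

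With the protocol's total of about 100, split 67/33, the shifts are 100/67 = 1.5 and 100/33 = 3.0 points.

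**5. Weight of one subject who exits early**

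Let e be the other recurrences, n the arm size including this subject, and p = e/(n − 1). Assume no other exclusions.

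- Protocol 4.8: (e + 1)/n
- SAP 2.4: e/(n − 1) = p
- Difference: (1 − p)/n, which is never negative

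The documents give no expected recurrence rate. Over p from 0 to 1, the shift runs from 2.0 down to 0 points (n = 50) and from 4.0 down to 0 points (n = 25). As an assumption, take the recurrence rates implied by the small randomized study cited in protocol section 2, (13 − 9)/13 = 4/13 and (14 − 4)/14 = 10/14:

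- Denervation arm: (1 − 4/13)/50 = 1.4 points
- Control arm: (1 − 10/14)/25 = 1.1 points

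**6. How many subjects?**

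Neither document gives a re-ablation rate or the share without a countable episode, so the count cannot be derived.

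**The case against.** The strongest reply is that the SAP follows the protocol's own primary-analysis section. Protocol 7.4.1 requires a documented episode and has no re-ablation term. The 4.8 sentence appears once, in a section on re-treatment, with no event date and no time limit. It could be read as saying only that re-treatment does not erase the recurrence that prompted it. This largely stands. A reader might infer that the SAP departs from a settled protocol definition. The documents do not support that, because the protocol itself has two versions. What remains is that 4.8 says in plain words that the procedures count, and SAP 2.4 uses the rest of 4.8 without that rule.

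A second reply is that nearly every re-ablated subject will already be an event: any countable episode after blanking suffices, and a 12-lead ECG counts at any duration. This stands, and it limits the size.

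A third is that the SAP defers to the protocol: "For any other terms, please consult the RD+AF clinical investigation plan". This does not repair the gap. The pointer is for terms the SAP leaves undefined, and SAP 2.4 defines recurrence itself.

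A fourth is that the recurrence form might capture repeat ablations. Its content is not in the documents, so this can be neither confirmed nor excluded. The written criterion still requires an AF episode.

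A reader might also infer that the re-treatment blanking makes the problem large by hiding much of the follow-up. That blanking is set by protocol 4.8 and would be the same if the SAP copied the counting rule, so it is not a measure of this omission.

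**Conclusion.** The inconsistency is real and worth fixing before analysis; its expected effect is modest. For a subject re-ablated after the initial blanking period without a countable episode, SAP 2.4 and protocol 4.8 give different answers on the primary percentage, on the Kaplan-Meier first event if that analysis is run, and on the rates under SAP 2.5.3. The difference is always towards fewer recurrences under the SAP.

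Each such subject followed to 12 months is worth 2 points (n = 50) or 4 points (n = 25), assuming the SAP total of 75, a 2:1 split and full denominators. An early exit is worth less unless the recurrence rate is near zero. The number affected is probably small and may be zero.

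The documents do not support two further inferences. One is that the comparison between arms is biased in a known direction: nothing shows in which arm such subjects would fall, although each weighs about twice as much in the smaller control arm. The other is that the SAP contradicts the protocol on a repeat ablation inside the initial blanking period: the protocol leaves that case open.

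**What to change.** 1. **Protocol.** Reconcile 4.8 with 4.6 and 7.4.1, and align 4.7, 4.10.10 and 7.4.2.3. Say explicitly whether a repeat ablation inside the initial blanking period counts as a recurrence.
2. **SAP 2.4, and 2.5.3 by reference.** State that a repeat ablation after the initial blanking period is a recurrence, both in the percentage and as a Kaplan-Meier first event. Carry over the protocol's answer for a repeat inside the initial blanking period.
3. **Event date.** Neither document gives one. A workable choice is the date of the repeat procedure, unless an earlier countable episode exists, in which case that episode's date applies.

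The cost is one or two sentences in the SAP and one protocol clarification. No new data should be needed: 4.8 has repeat procedures follow section 4.4, which uses the Procedure form, and asks for additional recording. That the procedure date is on that form is an assumption, since the form is not shown. The change affects how the endpoint is counted, not whether or when a subject is re-treated.

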3.4 Randomization

Subjects will be randomized in a 2:1 allocation between concomitant cardiac ablation for atrial fibrillation and renal denervation compared to cardiac ablation for atrial fibrillation alone. Randomization will be stratified by each investigational site.

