#### 2.5.4 BP reduction

The mean reduction of office systolic BP, office diastolic BP, and ambulatory BP parameters at six (6) months will be analyzed by computing the reduction of BP measurements compared to baseline (6-month – baseline) for each patient with data available in both time points. The mean and standard deviation of the BP reduction will be summarized for each group.

Blood pressure parameters at 12 and 24 months post procedure will be calculated in the same way as described in the calculation of the reduction at 6 months.

The percentage of subjects achieving office SBP < 140 at 6 months visit will be computed for each group as follows:

Number of subjects achieving office SBP < 140 at 6 months visit \*100

Number of subjects with data available in 6 months visit

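### The SAP commits to per-arm summaries only: no between-arm difference or confidence interval is planned, although the stated purpose is a preliminary comparison with ablation alone

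*SAP*

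**What the plan says.** SAP 2.2 gives the reason for the sample size as "to complete a preliminary evaluation on whether or not concomitant renal denervation with the" study system plus cardiac ablation improves outcomes relative to ablation alone. Protocol 7.2 says the same, and the protocol's synopsis and section 3.1 state a comparative purpose too. Allocation is 2:1 and "Randomization will be stratified by each investigational site" (protocol 3.4).

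SAP 2.2 adds that "No formal power analysis or hypothesis test will be performed". The commitments that follow all stop at the arm:

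- General rule (SAP 2.3): "categorical data will be summarized using frequencies and percentages". Continuous data get mean, n, SD and minimum and/or maximum.
- Primary endpoint (SAP 2.4): "An overall percentage of subjects experiencing an event will be summarized for each randomization arm".
- Optional time-to-event summary (SAP 2.4): "Kaplan-Meier analysis may be performed to provide freedom from atrial fibrillation rates at one year for each randomization arm".
- Major adverse cardiac events (SAP 2.5.2) and AF recurrence at other time points (SAP 2.5.3): rates by arm or group.
- Blood pressure (SAP 2.5.4): "The mean and standard deviation of the BP reduction will be summarized for each group".

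On the total, SAP 2.2 says 75, protocol 7.2 says approximately 100, and SAP 2.1 and protocol 3.11 say up to 100. Both documents require at least 50 patients to have both procedures; protocol 7.2 and SAP 2.1 and 2.2 give two thirds of the cohort as the alternative.

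**The concern.** A randomised control arm is there to support a comparison. Without a test, the difference between arms with its interval is the result that addresses the stated purpose. It shows how much the study has learned and helps size a later trial. If the plan is followed as written, that estimate need never be produced.

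Prespecification would also settle which contrast is reported. SAP 2.4 leaves two candidates open, the percentage among patients with known 12-month status and the Kaplan-Meier rate, and SAP 2.6 permits ad hoc and as-treated analyses.

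**Working it through.** **1. What can be derived from the planned tables.**

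| Contrast | Planned inputs | Derivable? |
|---|---|---|
| Difference in AF recurrence percentage, with CI | counts and denominators per arm (SAP 2.3, 2.4) | Yes, but not committed to |
| Unadjusted difference in mean BP change, with CI | n, mean, SD per arm (SAP 2.3, 2.5.4) | Yes, but not committed to |
| Interval for a Kaplan-Meier difference | rates only, and optional | No: standard errors are not listed |
| Baseline-adjusted BP difference | change summaries per arm | No: needs patient-level data |

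**2. The plan's own sample-size arithmetic.** No alpha, power or target effect is given, so no power formula can be checked; only the allocation can. 2/3 × 75 = 50, which matches the stated minimum. 2/3 × 100 = 66.7, which does not. So the minimum of 50 equals two thirds of the cohort only at a total of 75. The two ends of the range are 50:25 and about 67:33.

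**3. Precision of the missing contrast.** For each arm take the Wilson 95% limits (l, u) around p. The Newcombe limits for d = p1 − p2 are

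lower = d − √[(p1 − l1)² + (u2 − p2)²], upper = d + √[(u1 − p1)² + (p2 − l2)²].

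At 50% AF-free in both arms (assumed) and 50:25, the Wilson limits are 0.366 to 0.634 and 0.318 to 0.682. The half-width is √(0.1336² + 0.1825²) = 0.226.

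| Arms | AF-free (assumed) | Difference, points | 95% Newcombe, points |
|---|---|---|---|
| 50:25 | 50% v 50% | 0 | ±22.6 |
| 67:33 | 50% v 50% | 0 | ±19.9 |
| 45:22 (assumed 10% loss) | 50% v 50% | 0 | ±23.8 |
| 60:30 (assumed 10% loss) | 50% v 50% | 0 | ±20.8 |
| 50:25 | 60% v 45% | +15.0 | −8.4 to +36.4 |
| 67:33 | 60% v 45% | +15.0 | −5.5 to +34.0 |

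Because AF freedom is 100 minus the recurrence percentage, the same intervals apply to recurrence with the sign reversed. Moving from 75 to 100 patients narrows the half-width by 22.6 − 19.9 = 2.7 points.

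**4. The small randomised study cited in protocol section 2.** 9/13 = 69.2% and 4/14 = 28.6%, a difference of 40.7 points with a Newcombe interval of +3.2 to +65.4. This only shows what an interval adds. The 29% counts patients who were AF-free on no antiarrhythmic drugs, whereas this trial's definition carries no drug condition: "AF Recurrence is defined as episodes lasting longer than 30 seconds in duration unless detected via 12-lead EKG". The pair is therefore not a forecast for this trial.

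**5. What baseline adjustment would gain for BP.** The ratio of ANCOVA variance to change-score variance is (1 − r²)/(1 + k² − 2rk), where r is the baseline to follow-up correlation and k is baseline SD divided by follow-up SD. Both are assumed; neither document gives them.

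| k | r = 0.3 | r = 0.5 | r = 0.7 |
|---|---|---|---|
| 1.0 | 0.65 | 0.75 | 0.85 |
| 0.7 | 0.85 | 0.95 | 1.00 |

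A k below 1 is plausible because protocol 3.7.1 requires office systolic pressure of at least 140 mmHg at entry, which truncates the baseline distribution. The variance reduction therefore runs from none to 35% over these values.

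**The case against.** The strongest reply is that this is a declared descriptive feasibility study. The primary objective (protocol 3.2 and 7.4.1, SAP 2.4) is worded as feasibility of the combined procedure, not as a contrast between arms. The comparative wording sits in the purpose and sample-size text, mostly qualified as preliminary. This carries weight: the gap is one of estimation and reporting, and it does not invalidate anything planned. It does not close the gap, because an interval is not a test and the SAP bases its sample size on the comparative purpose.

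A reader might infer that the plan would publish bare percentages that conceal the imprecision. The documents do not support that. SAP 2.3 commits to frequencies as well as percentages and SAP 2.4 defines the numerator and denominator, so anyone can compute the unadjusted interval. Likewise, protocol section 2 reports the cited study with its counts and a p-value.

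A reader might also infer that the missing test or power analysis is the defect, or that the two totals undermine the design. Neither follows. The plan openly declines a test, and no decision rule depends on the total.

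Two smaller objections stand. The two contrasts that cannot be derived are an optional analysis and a secondary endpoint, and the gain from adjustment may be nil. A Newcombe interval also ignores the stratification by site, and it describes sampling error only. It says nothing about dropping event-free early exits from the denominator (SAP 2.4), or about leaving out denervation-arm patients in whom the system never entered the body (SAP 2.2).

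**Conclusion.** The point holds as an omission. The purpose is comparative and the design is randomised, but neither document commits to a between-arm estimate or its precision. 

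The missing interval would be wide: about ±23 points at 50:25 and ±20 at 67:33, or ±24 and ±21 with an assumed 10% loss. These figures assume 50% AF freedom in both arms, and other rates will change them somewhat. An observed 15-point advantage (60% v 45%) would be compatible with anything from modest harm to a large benefit at either size. No planned output is biased.

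The change should be made because it answers the stated question at almost no cost. The mismatch in totals is a real textual inconsistency, worth under 3 points of half-width, and needs only reconciliation.

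**What to change.** - **SAP 2.4.** Add the between-arm difference in the 12-month AF recurrence percentage (equivalently AF freedom) with a 95% Newcombe CI. Name it as the main contrast and label it as estimation without a hypothesis test. If Kaplan-Meier is run, add the difference in one-year rates with a 95% CI from Greenwood standard errors, as supportive.
- **SAP 2.5.4.** Add the between-arm BP difference at 6, 12 and 24 months with a 95% CI, adjusted for the baseline value already collected. If the sponsor wants no model, the unadjusted difference in mean change with its CI is an acceptable minimum.
- **Both sections.** State that the intervals reflect sampling error only, given the SAP 2.4 denominator and the Primary Analysis population.
- **Protocol 7.2, SAP 2.1 and 2.2 (minor).** Give one consistent statement of the total, for example 75 (50:25) as the minimum and 100 (67:33) as the maximum.

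The cost is a few lines of SAP text and code. No new data are needed. The results will look less certain than percentages shown side by side, and the precision gained from baseline adjustment may be close to zero.
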